- d. **Data collection:** Data used for investigating both our primary and exploratory research questions are obtained from the *Participant Questionnaire* administered at the beginning of ninth grade, beginning of tenth grade, and beginning of eleventh grade. The questionnaire is used to collect data on study participants' self-reported sexual behavior and experiences; intentions, thoughts, and feelings related to sexual behaviors; peer influence on sexual decision making; educational and career-related goals; intentions and feelings related to school; and social-emotional skills. It is administered three times at the following time points:
- a. Baseline – at the beginning of ninth grade just prior to the participant receiving their assigned intervention
 - b. 10th grade – at the beginning of tenth grade³
 - c. 11th grade – at the beginning of eleventh grade

While we collect data at three times over a period of two years, our analysis of primary research questions is concerned only with data gathered at baseline and tenth grade.⁴ Exploratory research questions will investigate mediating factors, subgroup effects, and other, behavioral outcomes.

Study participants who are offered *PGC* and class-as-usual receive the same questionnaire. The questionnaire contains 132 items and takes approximately 45-60 minutes to complete. The instrument was constructed by PRG staff and is composed of items and scales that have been used in previous research on sexual behaviors and contraceptive use. The instrument was reviewed by health professionals and pilot-tested by youth with similar characteristics to our proposed study population. The questionnaire includes the same items at each time point and will measure the same constructs with identical measures at each administration.

There are no differences in data collection procedures for treatment and control groups. Data collection is conducted identically for both groups.

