at the beginning of tenth grade. We describe below the specific operationalization of these three outcome measures (see Table 1 in Appendix for additional detail).

Sexual initiation

Sexual initiation is constructed as a dichotomous variable – participants are either coded as having ever had sex or not having ever had sex. Data used to assess the impact of the treatment (*PGC*) on sexual initiation are obtained from the following item on the *Participant Questionnaire*, which is administered to both treatment and control groups at baseline and the beginning of tenth grade:

- *Have you ever had any type of sex (oral, vaginal, or anal)?*

Persons who select *Yes* to the question are coded as 1, indicating that they have had sex. Persons who select *No* to the question are considered to not have ever had sex and are coded as 0 .

PGC will be considered to have a positive impact on sexual initiation if, as compared to participants who are assigned to the control group, a smaller proportion of participants who are offered *PGC* report sexual initiation at the beginning of tenth grade and the difference between groups is statically significant.

Times having sex

Times having sex is constructed as a continuous variable – the number of times in the past three months a participant engages in any type of sex (vaginal, oral, or anal).⁵ Data used to assess the impact of the treatment (*PGC*) on frequency of sex are obtained from the following item on the *Participant Questionnaire*, which is administered to both the treatment and control groups at baseline and the beginning of tenth grade:

- *In the past three months, how many times have you had any type of sex?*

Persons who indicate that they have never had any particular type of sex (vaginal, oral, or anal) or have not had any type of sex in the past three months are coded as having sex zero times.⁶

PGC will be considered to have a positive impact on times having sex if, at the beginning of the tenth grade, participants assigned to *PGC* report having sex fewer times than participants assigned to the control condition and the difference between groups is statically significant.

Number of sexual partners

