Number of sexual partners is constructed as a continuous variable – the number of sexual partners the participant reports that they have had in the past three months. Data used to assess the impact of the treatment (*PGC*) on number of sexual partners are obtained from the following two items on the *Participant Questionnaire*, which is administered to both the treatment and control groups at baseline and the beginning of tenth grade:

- The first question asks: *During your life, with whom have you had sexual contact?*

⁵ We are interested in exploring the effect of *PGC* on reduction of STI risk. Since STIs can be transmitted through any type of sexual contact (i.e., vaginal, anal, or oral), our measure of times having sex is not limited to sexual intercourse but includes all self-reported sexual activity.

⁶ The *Participant Questionnaire* contains sexual behavior questions that use a three-month recall period. As research has consistently found that memory of behaviors/events decreases over time and accuracy of recall is negatively associated with length of recall period (Clarke et al. 2008; Schwarz and Oyserman 2001), we use items with three-month recall periods to construct our measures of sexual behaviors since these should elicit more accurate responses than a longer recall period (e.g., six-month).

- If respondents select *Females*, *Males*, or *Females and males* to the first question, they are then asked this second question: *How many sexual partners have you had in the past 3 months?*⁷

Persons who indicate that they have never had sexual contact or have not had any sexual partners in the past three months are coded as having zero sexual partners.

PGC will be considered to have a positive impact on number of sexual partners in the past three months if participants assigned to *PGC* report fewer sexual partners at the beginning of tenth grade than participants assigned to the control condition and the difference between groups is statically significant.

- b. **Analytic sample:** In New York and North Carolina, 18 high schools are participating in the study and have supported the consent/assent, eligibility assessment, and enrollment processes for incoming ninth grade students (as described in section 3a above).

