- Race²¹
- Hispanic/Latino

Baseline Outcome Measures

In addition to the demographic measures, we will assess baseline equivalency of the outcome measures. We provide details on variable coding below; details on variable construction can be found in Table 2 in the Appendix.

- *Sexual initiation* at baseline (dichotomous; where 0=has never had sex and 1=has had sex)

¹⁹ Age is calculated using the baseline questionnaire completion date minus the participant's reported date of birth.

²⁰ At baseline, participants are asked "Which of the following best describes you?" and provided with a list of the following response options: *Female, Male, Transgender, Unknown, Other (please specify)*. Responses are recoded into the following categories: *Female, Male, Other* (which includes individuals who report *Transgender, Unknown, or Other*). For analysis, dummy variables are created for each category in the recoded variable.

²¹ At baseline, participants are asked "What is your race?" and are provided with a list of the following response options: *White; Black or African American; Hispanic, Latino, or Spanish origin; American Indian or Alaskan Native; Asian; Native Hawaiian/Other Pacific Islander; Unknown; or Some other race/ethnicity*. Participants can select more than one category and they can also specify some other race/ethnicity. This item is used to create two separate categorical variables. Hispanic/Latino is a dummy variable that indicates whether someone identifies as *Hispanic, Latino, or of Spanish origin* or not. Race is a categorical variable that indicates a person's self-identified race; responses are recoded into the following mutually exclusive categories: *White only, Black only, Other race only* (which includes *American Indian/Alaskan Native, Asian, Native Hawaiian/Other Pacific Islander, Other*), *Race not selected* (individuals who selected no racial category), and *Multiracial* (which includes individuals who selected more than one racial category). For analysis, dummy variables are created for each category in the recoded variable.

- *Times having sex in the past 3 months* at baseline (continuous; values range 0 to k , where 0= has had sex 0 times in past 3 months and k = number of times having sex in past 3 months)
- *Number of sexual partners in the past 3 months* at baseline (continuous; values range 0 to k , where 0= has 0 sexual partners in past 3 months and k = number of sexual partners in past 3 months)

Balance Assessment Methods

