²⁷ In the OAH Impact Analysis Plan guidance for Cohort 2 Tier 2B grantees, crossover is described as occurring "when individuals randomly assigned to the intervention or counterfactual conditions are later found to be receiving the services intended to be offered to the other condition." Given this, we calculate crossover in our sample as participants assigned to the treatment condition who only received class-as-usual and did not receive any PGC outreach sessions, as this is the intended counterfactual condition.

²⁸ In the OAH Impact Analysis Plan guidance for Cohort 2 Tier 2B grantees, contamination is described as occurring "when individuals assigned to the counterfactual condition end up receiving all or portions of the conditions intended only as part of the intervention." Given this, we calculate contamination in our sample as participants assigned to the control condition who received any amount of PGC programming, as this is the intended treatment condition.

- i. **Model specification and covariates:** The primary research questions under investigation in this study are whether offering *PGC* to participants impacts their: (1) reported sexual initiation; (2) reported times having sex; and (3) reported number of sexual partners (see Table 1 in Appendix for variable constructions). We propose to estimate these impacts using a regression that will model intervention effects as a function of assignment to *PGC* (i.e., Treatment), relevant baseline covariates, a baseline measure of the outcome variable, and school-level (blocking) indicators (see Table 2 in Appendix for variable constructions).²⁹ Although a straight difference-of-means approach should provide unbiased estimates of the effect of the treatment, we propose a model-based approach because it will increase the precision of those estimates. The empirical model will be estimated with an OLS regression (using Stata).³⁰ We present the empirical model here:

$$Y_{Post} = \beta_0 + \beta_1 T + \beta_2 Y_{Pre} + \sum (\beta_p X_p) + \varepsilon$$

Where:

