Y_{Post} – The outcome variable of interest, either: 1) sexual initiation; 2) times having sex in the past 3 months (continuous; values range 0 to k , where 0= has had no sex in past 3 months, and k = number of times having sex in past 3 months); or 3) number of sexual partners in the past 3 months (continuous; values range 0 to k , where 0= has 0 sexual partners in past 3 months, and k = number of sexual partners in past 3 months) reported by participant i at the 10th grade follow-up. (see Table 1 for full details on the variable construction).

Y_{Pre} – The baseline measure of the outcome variable of interest reported by participant i at baseline (see Table 2 for full details on the variable construction); variable will be re-centered at the grand mean for analysis.

T – A dummy treatment indicator variable whose value equals 1 if the participant is randomized into the treatment group and zero otherwise.

X – A p vector of baseline (i.e., measured prior to receiving intervention or exogenous to treatment) participant-level covariates as well as blocking variables to account for the variation in outcomes associated with these groups. These covariates, listed in detail in Table 2 in the appendix, will include:

- a) Age – age (based on date of birth) reported by participant at baseline (continuous); variable will be re-centered at the grand mean for analysis.

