Times having sex	
The risk outcome is operationalized as the number of times in the past three months a person reports having any type of sex.
 
The measure is calculated from the following items:
 
 • In the past 3 months, how many times have you had vaginal sex? • In the past 3 months, how many times have you had oral sex? • In the past 3 months, how many times have you had anal sex? 
The measure is calculated by summing the total number of times a person reported having vaginal, oral and anal sex in the past three months.
 
The resulting variable is continuous with values that range from 0 to k, where 0 indicates that a person has not engaged in sex in the past three months, and k indicates the number of times the person has engaged in sex in the past three months.
	Times having sex is included in the primary impact analysis as the pre-intervention or baseline measure of the behavioral outcome; it is included in the models so that individual-level change or difference can be assessed at the 10 th grade follow-up.
Number of sexual partners	
The risk outcome is operationalized as the number of sexual partners in the past three months.
 
The measure is calculated from the following item:
 
 • How many sexual partners have you had in the past 3 months? 	Number of sexual partners is included in the primary impact analysis as the pre-intervention or baseline measure of the behavioral outcome; it is included in the models so that individual-level change or difference can be assessed at the 10 th grade follow-up.

Covariate	Description of the covariate and how it will be used as a covariate in the analysis	Rationale for inclusion
	
The measure is calculated by summing the total number of sexual partners reported by the participant.
 
The resulting variable is continuous with values that range from 0 to k, where 0 indicates that a person has had no sexual partners in the past three months, and k indicates the number of sexual partners in the past three months.
	
Individual level covariates		

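### As written, the two count models carry only their own three-month baseline count as a measure of baseline sexual behaviour, so lifetime experience, already collected, is left out and some precision is lost

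*Combined protocol and SAP*

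**What the plan says.** The primary analysis (section 4f.i) is an OLS regression of the tenth-grade outcome on treatment and "relevant baseline covariates, a baseline measure of the outcome variable, and school-level (blocking) indicators". In the equation this becomes one baseline term Y_Pre and a vector X. Y_Pre is defined as "The baseline measure of the outcome variable of interest reported by participant i at baseline". X is introduced with "These covariates, listed in detail in Table 2 in the appendix, will include", and items a to e are then age, gender, race, Hispanic/Latino and school. Appendix A, Table 2 has rows for all three baseline behaviours, but the rationale for each ties it to its own outcome, for example "Times having sex is included in the primary impact analysis as the pre-intervention or baseline measure of the behavioral outcome".

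Both counts use a three-month recall period (section 4a). Students who say they have never had sex or "have not had any type of sex in the past three months are coded as having sex zero times". Students with no lifetime sexual contact or who "have not had any sexual partners in the past three months are coded as having zero sexual partners".

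Lifetime experience is recorded: section 4d lists sexual initiation "at baseline (dichotomous; where 0=has never had sex and 1=has had sex". None of the six sensitivity analyses in 4f.iv adds it to a count model. The plan justifies regression adjustment by precision (4f.i and its footnote 29), since a plain difference of means should already be unbiased.

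**The concern.** A baseline count of 0 pools two kinds of student: those with no sexual experience and those with experience but no activity in the last three months. It is reasonable to expect these groups to differ in recent activity a year later. No other listed covariate records lifetime experience, so the fitted model must give both groups the same prediction apart from demographics and school. Variation that a collected 0/1 variable could explain stays in the residual and widens the standard error of the treatment effect. This affects two of the three primary tests, in a trial that did not reach its 2,000-student target and whose Evaluation Abstract expects about 1,600.

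**Working it through.** **No stated figure to reproduce.** The documents give no power, effect size, SD, baseline rate, R² or attrition assumption. Every rate below is an assumption.

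**Inputs from the documents.** One Y_Pre per model and items a to e (4f.i); zero coding of both counts (4a); baseline initiation coded 0/1 (4d, Table 2); two-sided 0.05 (4f.i); 1:1 allocation (3b); about 1,600 students (Evaluation Abstract).

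**Formulas.**
- Variance saving s = 1 − (1 − R²_with ever-sex)/(1 − R²_own baseline only)
- SE ratio = √(1 − s)
- Equivalent N = 1600/(1 − s)

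**Hand check for partners, reduced to any/none.** Assume 20% experienced, half of them recently active, and follow-up activity of 12% (never), 45% (experienced, not recent) and 65% (recent).
- Own baseline only: students scoring 0 are 0.90 of the sample, with mean (0.80×0.12 + 0.10×0.45)/0.90 = 0.1567. Residual variance = 0.90×0.1567×0.8433 + 0.10×0.65×0.35 = 0.1189 + 0.0228 = 0.1417.
- With ever-sex added: 0.80×0.12×0.88 + 0.10×0.45×0.55 + 0.10×0.65×0.35 = 0.0845 + 0.0248 + 0.0228 = 0.1320.
- Ratio 0.1417/0.1320 = 1.073, which is worth about 7.3% more students, or about 117 at N = 1,600.
- Pessimistic case (10% experienced, half recent; 12/30/50%): 0.1196 falls to 0.1180, a gain of about 1.3%.

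**Simulation with full counts.** OLS on populations of 1,000,000, over ever-sex at baseline 10/20/30%, no recent sex among the experienced 30/50%, and follow-up activity (never / experienced not recent / recent) of 12/30/50%, 12/45/65% or 8/55/75%. Demographics and school were not simulated.

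| Outcome | Scenario | R² own → with ever-sex | s | SE smaller by | Extra students at 1,600 |
|---|---|---|---|---|---|
| Partners | lowest | 0.047 → 0.062 | 1.5% | 0.8% | 24 |
| Partners | 20%, 50%, 12/45/65 | 0.086 → 0.151 | 7.2% | 3.7% | 123 |
| Partners | highest | 0.146 → 0.292 | 17.1% | 9.0% | 330 |
| Times | lowest | 0.041 → 0.042 | 0.06% | 0.03% | 1 |
| Times | 20%, 50%, 12/45/65 | 0.074 → 0.084 | 1.05% | 0.5% | 16 |
| Times | highest | 0.125 → 0.150 | 2.8% | 1.4% | 46 |

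The times gain is small because the skew of the count dominates its residual variance. Adding the other baseline count as well raises the maximum only to 3.4% (times) and stays at 17.1% (partners).

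**Scale.** With N = 1,600, no attrition and no adjustment, the effect detectable at 80% power is (1.960 + 0.842)×√(4/1600) = 0.140 SD. A 5% variance saving gives 0.140×√0.95 = 0.137 SD, or 82.0% power at the same effect. A 10% saving gives 0.133 SD, or 84.0%.

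**Initiation model.** Nothing comparable is lost here. Recanted lifetime reports are set to missing at both waves (4c.iv), so a student experienced at baseline who stays in the analysis must score 1 at follow-up, and inexperienced students have zero counts. Adding a baseline count left R² unchanged at 0.531.

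**The case against.** An own-baseline ANCOVA with demographics and blocking indicators is a complete, pre-specified analysis. Randomisation keeps the treatment estimate unbiased without any further covariate. Both statements stand. A reader might infer from the pooled zeros that the effect estimate is biased or its estimand altered; the documents do not support that, because the omitted variable is a baseline one and the model is linear. Nor do the models adjust for a single variable: each also includes age, gender, race, ethnicity and school, which may absorb part of the gain computed above.

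The omission is also less than certain. Table 2 is headed as the covariates for the primary analyses and lists all three behaviours, X refers to Table 2, and section 4d (step 1, definition of the baseline variable) says each equivalence measure is a covariate in the analytic model. The equation, the definition of Y_Pre, items a to e and Table 2's rationales favour the own-baseline reading, but two analysts could fit different models.

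Three further limits stand. The size rests entirely on assumed rates. The partners item is gated by lifetime sexual contact (4a), a different question from 'ever had any type of sex', so the latter does not separate the partners zeros exactly. And the plan is dated January 2019, while Cohort 2 enrolled in 2017-2018 with tenth-grade follow-up intended a year later, so a covariate change may now come after outcome data were collected.

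**Conclusion.** The point holds as one of efficiency and clarity. On the likelier reading, both count models leave out a prognostic baseline variable that the study already holds, against the plan's own reason for adjusting. The forgone residual-variance saving is about 1.5% to 17% for partners and about 0% to 3% for times, so the practical case rests on the partners model. The direction was the same in every scenario; the size cannot be derived from the documents. It would be tempting to conclude that the missed enrolment target makes the omission decisive for power. That is not supported: no power calculation is given, and even a 10% saving only moves 80% power to 84%.

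**What to change.** In 4f.i and Table 2, state which baseline behaviours enter which model, and add baseline 'ever had sex' (0/1) to the times and partners models beside each model's own baseline count.

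Use the baseline answer as given, before the over-time recode in 4c.iv. That rule blanks a baseline report because of what the student says at follow-up. If the plan's dummy adjustment were then applied, the missing indicator would carry a post-randomisation response into the model for any recanter who still has a usable count. The indicator should mark only baseline nonresponse or invalid answers.

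A log-transformed count, an any-recent-sex term, and the intention and peer-influence scales are not needed: the first two add negligible precision and no gain has been computed for the scales.

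If outcomes by arm have already been seen, keep the benchmark model and report the added covariate as a labelled sensitivity analysis. The cost is one or two degrees of freedom, a few lines of text and a dated plan change, with no new data.
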